6.3.4 Embryo Transfer

Embryo transfer will follow the standard protocol in place at each clinical trial site. Data pertaining to the Day 3 or Day 5/6 embryo transfer procedure will be recorded on the **Transfer and Treatment Outcome** eCRF for all patients (Eeva and non-Eeva ones) including:

- Date and day of transfer
- Luteal phase support
- Use of ultrasound
- Final number of embryos transferred

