8.3 Added selection

The KID sample (Known Implantation Data) is the subset of ITT sample such that the IR=0% or 100% (for single,double or triple) mbryo transfer, ITT=KID; for other implantations, women such that $0 < IR < 1 < 2 < 3$ will be disregarded).

9 General Specifications for Statistical Analyses

10 Study Subjects

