14.1 Primary analysis

Implantation rate will be analyzed with two definitions

First definition: The IR (at embryo level) corresponding to a group of patients is calculated as the ratio of the total fetal sacs (nFS) identified by ultrasonography at weeks 5 to 8 divided by the number of embryos transferred (nET), thus $IR = nFS/nET$.

Alternative Definition of Implantation Rate: The previous (and usual) calculation of IR as mentioned in the protocol ($IR = nFS/nET$) has problems, in particular the implanted embryos are not independent. The international definition used by WHO in particular (see for instance <http://www.advancedfertility.com/ivf.htm>) is: The alternative definition IR^* at women level is $IR_w = nFS_w/nET_w$ and $IR^* = (1/n) \cdot \sum_{w=1,n} IR_w$.

Note: The two definitions IR and IR^* coincide in some cases, in particular for elective Single Embryo transfer eSET (where only one embryo is transferred) or when KID sample is used, but in the general case (ITT sample for instance, IR and IR^* will be different).

The point estimate and 95% CI of IR and IR^* will be calculated in both groups EMG and MG for the ITT selection. No inferential comparison will be conducted between these two groups (as this study is purely descriptive).

The following sections are considered as secondary analyses.

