14.6 Exploratory Variables

Multiple Linear regression analysis of IR (based on subject level) as dependent variable and treatment as independent parameter effected by the following confounding factors

Factors	Description
Stimulation protocol	Categorical variable, 3 states: Agonist Luteal phase; Antagonist; and Agonist Mirco-dose Flare and Other
Drugs used	Categorical variable, 3 states: recombinant Gn, urinary Gn, and mix-use of recombinant and urinary Gns
Day of transfer	Categorical variable, 2 states: D3 Vs D5/6
Age of patients	Continuous variable , years
Culture medium	Categorical variable, 5 states: Quinn's Advanced Fertilization, Global Medium, Vitro life G-IVF, Irvine Single Step Medium, and Other

A better estimate of implantation rate will be obtained based on subject level adjusted for confounding factors by a Multiple Linear regression.

Given the exploratory nature of the design, the model will be investigated stepwise and repeated backward. The final model will exclude backward P-values > 0.10.

The Center effect will also to be considered in the model.

The results of regression analysis will be reported with the following items

- Regression Coefficient with 95% CI
- Standard Error
- P-value
- Coefficient of Determination (R^2)

Subgroup analyses

Further subgroup analysis based on selected baseline parameter could be conducted as follows.

- 1) IR of the two treatment groups at each site (descriptive summary statistics with 95% CI,

and RR with 95% CI and P value). The Risk Ratio, 95% CI and P-value will be calculated, provided the number of subjects in a site will be at least 30, otherwise only descriptive statistics will be provided for that particular site.

- 2) IR, CPR, OPR and SMR of the two treatment groups for subgroups of patients with ET on D3 and D5/6 (descriptive summary statistics, RR with 95% CI and P value);
- 3) IR, CPR, OPR and SMR of the two treatment groups for subgroups of patients with age ≤35 and >35(descriptive summary statistics, RR with 95% CI and P value).
- 4) IR of the two treatment groups for subgroups of patients using 5 types of culture media (descriptive summary statistics, RR with 95% CI and P value).
- 5) IR of subgroups of patients using 5 types of culture media (regardless the method of embryo assessment, descriptive summary statistics and 95% CI)

15 Safety Evaluation

In conformity with protocol, device deficiency will be individually listed.

16 References

No reference at this stage

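### SAP 14.6 regresses each woman's implantation proportion with no robust variance, so standard errors are unreliable for terms related to number of embryos transferred; no adjusted rate per arm is listed

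*SAP*

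**What the plan says.** SAP 14.6 specifies a "Multiple Linear regression analysis of IR (based on subject level) as dependent variable and treatment as independent parameter", with stimulation protocol, drugs used, day of transfer, age and culture medium as covariates and centre also considered. Terms with P above 0.10 are removed backward. No weight, link function or robust variance is named.

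The purpose is stated as follows: "A better estimate of implantation rate will be obtained based on subject level adjusted for confounding factors by a Multiple Linear regression". Yet "The results of regression analysis will be reported with the following items" introduces only four: "Regression Coefficient with 95% CI", standard error, P-value and R-squared. The table list in SAP section 19 contains no adjusted rate either.

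The outcome is defined in SAP 14.1 as `nFS_w/nET_w` for woman w. The unweighted mean over women is `IR*`, introduced because "the implanted embryos are not independent". The denominator varies: SAP 8.3 provides "for single,double or triple" transfers, and Protocol 6.3.4 says "Embryo transfer will follow the standard protocol in place at each clinical trial site". The number transferred is recorded (`Nte`, SAP 17) but is neither a covariate nor a weight in 14.6.

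**The concern.** Ordinary linear regression computes its standard errors from one common residual variance. A proportion out of one embryo and a proportion out of two or three do not share a variance. If embryo number is related to a model term, the standard error for that term is biased, and so are its confidence interval and P-value. Because transfer practice is set by site, embryo number may well track centre. It may also track culture medium, which is likely to vary by laboratory, and day of transfer.

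Two things are at stake. The P-values choose which covariates adjust the treatment estimate, so a biased standard error changes the adjustment set. And the SAP presents this model as its route to an adjusted implantation rate, but a reader of the listed outputs would not find one. The treatment coefficient is a difference, and with age entered in years the intercept refers to age 0.

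**Working it through.** **The plan's own figure.** SAP 14.6 gives no number. The only design figure is the precision table in Protocol 7.2, and it reproduces with 1.96·√(p(1−p)/n). At p = 35%, n = 500 gives 4.18 points and n = 1000 gives 2.96, against 4.2 and 3.0 in the table. The other eight entries also agree to one decimal. The table thus gives each woman the variance p(1−p), which is that of a single transfer.

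**Inputs.** From the documents: one to three embryos per woman, 2:1 allocation (1000 and 500), removal at P > 0.10, and rates of 25–45% considered. Assumed, because the documents do not give them: p = 35%, within-woman correlation ρ of 0 to 0.3, and every embryo mix below.

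**Step 1: variance by embryo number.** With m embryos, Var = p(1−p)·[1+(m−1)ρ]/m.

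| ρ | m = 1 | m = 2 | m = 3 | Ratio, single to double |
|---|---|---|---|---|
| 0 | 0.2275 | 0.1138 | 0.0758 | 2.00 |
| 0.15 | 0.2275 | 0.1308 | 0.0986 | 1.74 |
| 0.3 | 0.2275 | 0.1479 | 0.1213 | 1.54 |

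**Step 2: effect on a two-level factor.** Let the minority level have share q and variance v₁, and the other level v₀. Per woman:
- Model variance: [q·v₁+(1−q)·v₀]·[1/q+1/(1−q)].
- True variance: v₁/q + v₀/(1−q).
- SE ratio r = √(model/true).
- Coverage of a 95% CI: 2Φ(1.96r)−1.
- Chance that a null term survives the 0.10 cut-off: 2[1−Φ(1.645r)].

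Worked case, with q = 10%, single transfers 80% in the minority and 30% elsewhere, and ρ = 0.15:
- v₁ = 0.8(0.2275)+0.2(0.1308) = 0.2082.
- v₀ = 0.3(0.2275)+0.7(0.1308) = 0.1598.
- Model variance 1.830, true variance 2.259, so r = 0.90.

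| q | Single transfers, minority vs rest | r | Coverage | Null term kept |
|---|---|---|---|---|
| 10% | 70% vs 40% | 0.94 | 93.4% | 12.2% |
| 10% | 80% vs 30% | 0.90 | 92.2% | 13.9% |
| 5% (one of about 20 sites) | 80% vs 30% | 0.89 | 91.8% | 14.4% |
| 10% | 100% vs 0% | 0.80 | 88.5% | 18.6% |
| 10% | 30% vs 80% | 1.11 | 97.1% | 6.8% |
| 10% | 0% vs 100% | 1.25 | 98.5% | 4.1% |

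**Step 3: the arm coefficient.** Here the shares are 2/3 and 1/3. With Eeva at 70% and control at 40% single transfers, v is 0.1985 and 0.1695. The model variance is 0.1888·4.5 = 0.850, the true variance is 0.1985·1.5 + 0.1695·3 = 0.806, and r = 1.03. With the arms swapped, r = 0.97. With equal mixes, r = 1.00.

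**Step 4: simulation.** There were 3000 runs per scenario, with 1000 and 500 women, a model containing treatment, day of transfer and age, and ρ of 0 to 0.2.
- Treatment coefficient, same mix in both arms: SE ratio 0.99–1.00, coverage 94.3–94.9%.
- Treatment coefficient, 70% vs 30% single transfers in either direction: SE ratio 0.95–1.05.
- Treatment coefficient, one arm all single and the other all double: SE ratio 0.87–1.11, coverage 91.1–97.1%.
- Day coefficient, Day 5 using fewer embryos: 0.91–0.92 with 25% Day 5 transfers (coverage 92.4–93.3%), 0.99–1.00 with 50%, and 1.06–1.11 with 75%.
- HC3 standard errors: coverage 94.2–95.4% for both coefficients in every scenario.

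**The case against.** The strongest reply is that unequal variance biases these standard errors only for regressors related to the variance. Treatment is randomised, so unless Eeva changes how many embryos are transferred, its standard error is sound. A reader might infer from the missing robust variance that every interval and P-value in the model is wrong, including the Eeva-versus-control contrast. The documents do not support that, as steps 3 and 4 show. The 10–25% distortions belong to covariates, not to the arm.

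The sizes also rest on embryo mixes that appear in neither document. Even the direction for day of transfer is open, because neither document says which day will be the minority. That stands, and it is why a range is given.

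A reader might also infer that no adjusted rate will be produced. That goes too far: SAP 14.6 says one will be obtained, and in a linear model without interactions the listed treatment coefficient already is the adjusted difference. What remains is narrower: the rate per arm is not among the listed outputs.

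Finally, the section is exploratory, SAP 14.1 calls the study purely descriptive, and no decision rule depends on this model. This limits the importance but does not make the reported error bars valid.

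**Conclusion.** The point holds in a limited form. For terms related to embryo number, the model standard errors in SAP 14.6 are not valid. With p = 35%, ρ between 0 and 0.3 and plausible-to-extreme mixes, they are roughly 5–20% too small when the level with more single transfers is the minority, and too large in the reverse case. A null covariate could then be kept about 12–19% of the time instead of 10%, or less often than 10% in the reverse case. The arm coefficient is right to about 1% with similar mixes and about 3% off at 70% versus 40% single transfers. It is materially wrong only if the arms differ sharply in embryos transferred.

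Separately, and without any assumption, the adjusted implantation rate per arm that the section promises is not in its output list. The primary descriptive `IR` and `IR*` do not come from this model and are unaffected.

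**What to change.** In SAP 14.6:

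1. Keep the unweighted woman-level model, which matches `IR*`, but compute all standard errors, 95% CIs and P-values, including those used for elimination, with a heteroscedasticity-consistent (HC3) covariance.
2. Keep treatment in the model whatever its P-value. The section does not say so now. With no treatment effect, the 0.10 rule would remove it about 90% of the time, and adjusted rates per arm could not then be formed.
3. Add to the listed outputs the covariate-standardised `IR*` for EMG and for MG. This is the average model prediction over all women with the arm set to each value in turn, with a 95% CI from the same covariance. R-squared may stay, and the treatment coefficient already supplies the adjusted difference.

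The cost is a few sentences and a software option, with no new data. Some intervals become slightly wider and others slightly narrower. HC3 does not correct for computing intervals after backward selection; that is a separate limitation and should be stated with the results.

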5.3.1 Inclusion Criteria

For inclusion in the trial, **all** of the following inclusion criteria **must** be fulfilled:

1. All infertile patients treated with IVF/ICSI.
2. Patient age \leq 40 years.
3. \leq 3 failed IVF/ICSI cycles.
4. At least 4 normally fertilized eggs (2PN) in current cycle.
5. Normal uterine cavity.
6. Fertilization using only ejaculated sperm (fresh or frozen).
7. Subject must have read and signed the Informed Consent form.

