5.4 Documented variables

5.4.1 Screening and treatment

Inclusion Criteria, Age, Pregnancy History , Number of attempts , Number of Spontaneous abortions, Number of Live Births , Number of Non-ART cycles, Number of Fresh ART cycles, Number of Frozen ART cycles, Follicle Stimulating Hormone Maximum, Follicle Stimulating Hormone Units, Anti Mullerian Hormone Max, Anti Mullerian Hormone Unit, Estradiol Max, Estradiol Units, Luteinizing Hormone Max, Luteinizing Hormone Units, Antral Follicle Count ,

Male Infertility, Polycystic Ovaries, Reduced Ovarian Reserve, Tubal Factor , Unexplained, Other.

Treatment variables: Protocol of Stimulation, stimulation medication, Time of hCG trigger to oocyte retrieval, Pre-trigger Endometrium (Trt Set).

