8.1 Intention-to-treat (Full Analysis Set)

The intention-to-treat population includes all randomized subjects. Due to the fact that this is an exploratory trial in contrast to usual definitions of ITT ('presented as randomized') subjects will be presented based on the method used (EvMG = Eeva scores plus morphology grading, MG=morphology grading only).

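### The SAP 14.6 adjusted model has age as its only patient prognostic factor, although previous ART cycles, live births, infertility cause and antral follicle count are baseline variables; adding them is a small, nearly free improvement

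*SAP*

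**What the plan says.** SAP 14.6 regresses implantation rate at subject level on "treatment as independent parameter effected by the following confounding factors". The table that follows lists five:

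- stimulation protocol: "Categorical variable, 3 states: Agonist Luteal phase; Antagonist; and Agonist Mirco-dose Flare and Other"
- drugs used: "recombinant Gn, urinary Gn, and mix-use of recombinant and urinary Gns"
- day of transfer: "Categorical variable, 2 states: D3 Vs D5/6"
- age: "Continuous variable , years"
- culture medium, in five categories

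Centre is to be considered as well. Terms with P above 0.10 are removed backward, and no term is named as exempt. The SAP presents the result as an improved estimate of the implantation rate. It reports the coefficient with its 95% CI, standard error and P-value, and R².

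Among the variables documented at screening, SAP 5.4.1 names "Number of Fresh ART cycles, Number of Frozen ART cycles", live births, AFC and the causes of infertility. SAP 17 carries them in its baseline block as Pt2, Pt32, Preg4, AFC and RI1 to RI6. SAP 19.2.3 tabulates them by arm.

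On grouping, SAP 8.1 states that "subjects will be presented based on the method used". Protocol 5.5 and 7.3 describe 2:1 permuted blocks with a fixed block size and name no stratification factor; further detail is left to the EDC manuals.

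**The concern.** Four of the five listed factors are treatment or laboratory choices, and day of transfer is settled after enrolment on day 1 (Protocol 8.2). Only age describes the woman, and the P > 0.10 rule could remove even age. The SAP will display any difference between arms in reproductive history, cause or AFC in a baseline table, but no planned step carries that difference into an adjusted estimate. Neither document explains the omission.

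Three things are at stake, all within an exploratory model. Chance imbalance in these factors stays in the adjusted arm effect. A little precision is lost. And because groups follow the method used, randomisation does not fully protect the comparison, so measured prognostic factors would be of some help if women changed group for reasons linked to prognosis.

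**Working it through.** **The plan's own figure.** Protocol 7.2 gives half-widths of a 95% CI for one arm, which follow 100 × 1.96 × √(p(1−p)/n). At p = 35% this is 4.18 for n = 500 (stated 4.2) and 2.96 for n = 1000 (stated 3.0). All ten cells of the table reproduce after rounding.

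**Arm difference, unadjusted.** SE = √(0.35 × 0.65 × (1/500 + 1/1000)) = 2.61 points, so the half-width is 1.96 × 2.61 = 5.12 points. This treats per-woman implantation as binary and assumes that every woman has a transfer.

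**Precision by formula.** Added covariates with incremental R² multiply the SE by about √(1 − R²). The documents give no R², so this is a range:

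| Assumed incremental R² | Half-width (points) | SE reduction |
|---|---|---|
| 1% | 5.09 | 0.5% |
| 2% | 5.07 | 1.0% |
| 3% | 5.04 | 1.5% |
| 5% | 4.99 | 2.5% |
| 10% | 4.86 | 5.1% |

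**Precision by simulation.** Two sets of assumed effects were used, each with 1000 versus 500 women and least squares on a binary outcome, comparing age alone with age plus the omitted factors.

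1. Additive effects on a rate near 37%: −5 points per SD of age, −3 per previous cycle, +6 for a prior live birth (25% of women), −5 for one infertility cause (20% of women), +2 per SD of AFC. Over 1500 runs, R² rises from 1.5% to 2.7% and the SE falls from 2.603 to 2.595 points: 0.008/2.603 = 0.3%. The arm estimate moves by 0.23 points on average (95th percentile 0.58).
2. Larger effects in log-odds: −0.30 per SD of age, −0.25 per previous failed cycle, +0.35 for a prior live birth, +0.20 per SD of AFC. Over 400 runs, R² rises from 2.0% to 4.7% and the SE falls from 2.63 to 2.60 points: 0.03/2.63 = about 1%.

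The half-width therefore narrows by between 1.96 × 0.008 = 0.02 and 1.96 × 0.03 = 0.06 points. The first set used a single indicator for cause. Entering RI1 to RI6 as six indicators adds five terms, costing roughly 5/1500 = 0.33% of the variance, or about 0.17% of the SE, unless they predict outcome. At the low end, then, the precision gain is close to nil.

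**Chance imbalance.** For a binary factor of prevalence q, the 95% limit of the difference between arms is 1.96 × √(q(1−q)(1/500 + 1/1000)).

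- q = 30%: 4.92 points. With an assumed effect of 5 points on implantation, the arm difference shifts by 0.0492 × 5 = 0.25 points.
- q = 50%: 5.37 points. With an assumed effect of 15 points, the shift is 0.0537 × 15 = 0.81 points.

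Against a half-width of 5.12, that is 5% to 16%.

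**Grouping by method used.** The algebra can be done only with invented inputs. Suppose 5% of 1000 Eeva women are counted as controls and their rate is 10 points below that of the remaining Eeva women, with both arms at 35% overall. The remaining Eeva women are then at 35.5% and those moved at 25.5%. The control group becomes (500 × 35% + 50 × 25.5%)/550 = 34.14%, so the arm difference is 35.5 − 34.14 = 1.36 points with no true effect. Letting the share moved run from 2% to 10% and the gap from 5 to 15 points gives 0.29 to 3.75 points. Neither input is in the documents, so this shows sensitivity and is not an estimate for this trial.

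**The case against.** The strongest reply is that little depends on this model. SAP 14.1 plans no inferential comparison of the arms, and SAP 14.6 is exploratory. Under randomisation any imbalance is due to chance and the unadjusted interval already allows for it. The precision gain is tiny. Stimulation protocol and drugs may partly stand in for ovarian reserve, and the baseline table makes imbalance visible. All of this stands, and it is why the point is minor.

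A reader might also infer that the omission biases the comparison towards Eeva by around a point. The documents do not support that:

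- They give no rate of changing group and no link between such changes and maternal prognosis.
- Under SAP 8.2, a woman whose embryologist overrides Eeva stays in the Eeva group as non-conforming. The stated reason for overriding is a conflict with embryo morphology, not reproductive history or AFC.
- The other routes to a missing Eeva result, malfunction (Protocol 3) and imaging stopped early (SAP 17), are not tied to prognosis.
- A comparison against age alone is not a comparison with the planned model, which has four other candidate factors and centre.

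Nor is the regression the only safeguard. SAP 14.6 adds subgroup summaries by age and site, and eligibility narrows prognosis. The eligibility limit on "failed IVF/ICSI cycles" gives no reason, so it does not show that the trial regards past failure as prognostic. No count of failed cycles is listed either; Pt2 and Pt32 count previous cycles whatever their result.

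What remains is that a model presented as giving an improved estimate leaves out recorded prognostic factors without a stated reason.

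**Conclusion.** The point holds as a minor improvement. The omission is plain in the text and unexplained. Under the assumed effects, adding the factors cuts the SE of the arm effect by about 0.3 to 1% and adjusts for chance shifts of roughly 0.25 to 0.81 points per factor at the 95% limit. If grouping by method used moves women by prognosis, it would also give partial protection, of a size that cannot be derived from the documents. Covariates would not restore what randomisation provides; the grouping rule is a separate matter. The primary estimates do not change. Every effect size, prevalence and R² used here is an assumption.

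**What to change.** In SAP 14.6, pre-specify one adjusted model with these terms, all kept whatever their P-value:

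- treatment, centre and age
- number of previous ART cycles (Pt2 + Pt32)
- prior live birth (Preg4 > 0)
- infertility cause (RI1 to RI6)
- AFC

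Listing the new factors without exempting them from the P > 0.10 rule would not be enough. Report the treatment coefficient and its 95% CI beside the unadjusted difference.

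State the rule for missing AFC in advance. Protocol 6.3.1 does not name AFC among the baseline items and Protocol 7.6.1 rules out imputation, so without a rule, women with no AFC would drop out of the model. A missing category is simple, but harder to defend when groups are formed by method used; a run without AFC would show whether it matters.

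Keep the analysis of stimulation protocol and drugs: SAP 5.2 lists their relation to implantation outcomes as a secondary endpoint, and this regression is the only planned analysis that relates them to implantation.

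Cost: a few lines of SAP text and about ten degrees of freedom (1 + 1 + 6 + 1, plus 1 if AFC has a missing category) among about 1500 women. No new data are needed.

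### SAP 14.6 drops adjustment factors with P > 0.10 and then reports the survivors with ordinary 95% CIs and P-values, which are not valid after selection

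*SAP*

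**What the plan says.** SAP 14.6 (Exploratory Variables) specifies a multiple linear regression of subject-level implantation rate on treatment and five factors: stimulation protocol (3 states), drugs used (3), day of transfer (2), age (continuous) and culture medium (5). The stated purpose is an improved, covariate-adjusted estimate of implantation rate.

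On selection it says: "Given the exploratory nature of the design, the model will be investigated stepwise and repeated backward". The removal rule is: "The final model will exclude backward P-values > 0.10". A separate sentence follows: "The Center effect will also to be considered in the model".

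The listed outputs begin with "Regression Coefficient with 95% CI" and continue with the standard error, P-value and R-squared. The SAP states no post-selection correction, shrinkage or bootstrap and does not plan a full-model table. It does not say whether treatment or centre is exempt from elimination, or whether a multi-level factor is tested as a whole or level by level.

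**The concern.** The same data decide which factors stay and then supply their intervals and P-values. A weak factor is reported only when chance has made its estimate large. Its coefficient is therefore biased away from zero, and an interval computed as if the model had been fixed in advance is centred in the wrong place.

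This matters because Protocol 5.2 describes the trial as a source of hypotheses for a later randomised trial. In addition, SAP 5.2 lists stimulation protocol type in relation to implantation outcomes among the secondary endpoints. The 14.6 regression is the only analysis in the SAP that relates stimulation protocol or drug class to implantation, so readers will use its coefficients as effect sizes.

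**Working it through.** The documents give no operating characteristics for this rule, so there is no stated figure to reproduce.

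**Inputs from the SAP:** retention at P ≤ 0.10, so c = 1.645 for a single-df term; reported 95% CI, so ±1.96 SE. **Approximation:** the factor's estimate in SE units is Z ~ N(δ, 1), where δ is the true effect in SE.

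**Step 1, null factor (δ = 0).** Its P-value is uniform, so P(P < 0.05 | kept) = 0.05/0.10 = 50%. The 95% CI excludes zero exactly when P < 0.05, so its coverage given retention is also 50%.

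**Step 2, weak factor (δ = 1).**
- Kept: P(Z > 1.645) + P(Z < −1.645) = 0.2595 + 0.0041 = 0.264, or 26%.
- Mean when kept: δ + [φ(c − δ) − φ(c + δ)]/P(kept) = 1 + (0.3240 − 0.0121)/0.264 = 2.18, or 2.2 times the truth.
- Coverage when kept: the CI covers if Z lies between −0.96 and 2.96. Combined with Z > 1.645 this is [Φ(1.96) − Φ(0.645)]/0.264 = (0.9750 − 0.7405)/0.264 = 0.89.

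**Step 3, other effect sizes by the same formulas.**

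| True effect (SE) | Kept | Mean when kept ÷ truth | CI coverage when kept |
|---|---|---|---|
| 0 | 10% | – | 50% |
| 0.5 | 14% | 3.4 | 71% |
| 1 | 26% | 2.2 | 89% |
| 3 | 91% | 1.06 | 97% |

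**Step 4, simulation of the whole procedure.** N = 1500, 2:1, treatment forced in, the five factors with 2, 2, 1, 1 and 4 df, factor-level F tests, elimination at P > 0.10. Factor prevalences, an implantation rate near 33% and one or two embryos transferred are assumptions; centre was not simulated. With 4000 trials per scenario, each noise factor was kept in 9.9% to 10.1% of trials, and 49% to 50% of those kept had P < 0.05 (48% to 53% across all runs made). If multi-level factors are read by individual coefficients, the share of kept noise factors with at least one coefficient at P < 0.05 rises to 65% (all five noise) or 76% (three noise).

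**Step 5, does selection create more false leads than a full model?** Chance of at least one noise factor with P < 0.05:
- All five noise: 22.5% full model, 22.3% backward (second run 22.1% and 22.9%); analytic 1 − 0.95^5 = 22.6%.
- Age and day of transfer prognostic, three noise: 13.1% full, 13.7% backward (second run 13.5% and 13.8%).

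There is no material difference.

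**Step 6, effect on the treatment estimate when treatment is forced in.** Type I error is 5.3% to 5.4%. Selected and full-model estimates differ with an SD of 0.06 to 0.07 SE. CI coverage is 95.3% to 95.6% with selection and 95.5% to 95.7% without.

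**Step 7, is selection needed to save parameters?** Factor df: 2 + 2 + 1 + 1 + 4 = 10. With about 20 centres (19 df), treatment and intercept, the full model has 10 + 19 + 1 + 1 = 31 parameters, and 1500/31 ≈ 48 subjects each. With the 22 sites of Protocol 5.1 it is 33 parameters and about 45 each.

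**The case against.** The case for leaving the rule alone is substantial. The SAP gives the exploratory design as its reason for selection, the regression sits below the primary analysis, and SAP 14.1 plans only point estimates and CIs by arm. No primary estimate depends on the rule.

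Three stronger readings are tempting, and the evidence supports none of them.

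- **That half of all noise factors will look significant, or that selection multiplies false leads.** The 50% is conditional on a factor being null and kept. Unconditionally, a given null factor is reported as significant in about 5% of trials, and Step 5 shows that the full model yields about as many spurious findings.
- **That the adjusted arm comparison is left to chance.** Step 6 shows that it barely moves if treatment is forced in. The SAP does not say that treatment is forced in, and should.
- **That centre will be eliminated.** The SAP says only that it will be considered, in a sentence separate from the removal rule.

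The SAP also does not forbid showing the full model; it simply does not plan it.

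All of that stands. It does not rescue the reported intervals. An exploratory label allows looser error control across many looks, but it does not give a selected coefficient's interval 95% coverage, and the SAP lists that interval as an output with no caveat specific to selection.

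**Conclusion.** The rule as written gives invalid intervals and inflated coefficients for weak or null factors that survive elimination. Coverage when kept is 50% at a true effect of 0, 71% at 0.5 SE and 89% at 1 SE, with 2.2-fold inflation at 1 SE. At 3 SE or more the effect is minor: 6% inflation at 3 SE, and coverage not below nominal.

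The consequence is over-reading of individual factor results, with null results left out. It is not a larger number of false positives, a distorted primary estimate or a distorted treatment effect. The analytic figures rest on a normal approximation for a single-df term; the simulated figures rest on the assumptions in Step 4. How many of the five factors are truly weak is unknown. Age and day of transfer may well be prognostic, in which case the problem falls mainly on stimulation protocol, drug class and culture medium.

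**What to change.** In SAP 14.6:

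1. Delete the sentence on stepwise and backward investigation and the sentence setting the 0.10 removal threshold.
2. Specify one model in advance: treatment, the five factors already listed (10 df) and centre, all kept regardless of P-value.
3. Report every term with its coefficient and 95% CI.
4. If a reduced model is also shown, label it descriptive and give no CIs or P-values for it.
5. Add a covariate for previous cycles only if it is defined from the fresh and frozen ART cycle counts in SAP 17, which holds no count of failed cycles. Otherwise leave it out.

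When fixing the model, state how centre enters. Protocol 5.6 keeps culture conditions the same for all embryos within a laboratory. If each centre uses a single medium, which the documents do not settle, fixed centre terms and culture medium cannot both be estimated, and the SAP should say what is done then.

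The cost is SAP wording and a few degrees of freedom out of a planned 1500 subjects. No new data are needed. The fixed model gives each reported interval its nominal coverage, to the extent that the linear model itself is adequate. It is not expected to reduce the number of spuriously significant factors.
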